13.1 Overview

This phase 2 single site study in cashew or shrimp-allergic children and adults intends to identify basic immune mechanisms that explain the effects of OIT in individuals who do or do not become clinically tolerant and to determine whether immune monitoring can predict safety and outcomes in OIT protocols. We will rely on analysis of covariance (ANCOVA) methods to model the change of CD28 expression measured at week 52 from baseline as a continuous variable as a function of: the change of CD28 measurement from the baseline and an indicator for whether the subject passed the DBPCFC at week 52, where the parameter for the latter is of main

interest and represents whether changes in expression of CD28 differ for those who achieve desensitization versus those who do not. In addition, methods appropriate for right-censored data (time to achieving desensitization) such as the Cox proportional hazards model also will be considered. We also will use methods such as the Least Absolute Selective Shrinkage Operator (LASSO) to identify immunophenotypes that correlate with clinical outcomes, and to identify epitopes and/or clonotypes associated with clinical phenotypes. Such methods are appropriate when jointly considering a large number of correlated features, as we anticipate with data generated from the CyTOF platform. Finally, we will consider hierarchical clustering techniques to explore the clustering of both mechanistic features and patients, to provide insight into whether mechanistic features can be used to describe clinical phenotypes of interest.

13.2 Endpoints and anticipated results

13.2.1 Primary Endpoint(s)/Outcome(s)

Change in expression of CD28 in the CD4+ allergen specific (CD154+) T-cells at 52 weeks relative to baseline values between those who do and do not pass the DBPCFC at week 52 at a cumulative tolerated dose of 2043 mg.

i.e. Comparing those who pass the desensitization challenge vs all others there will be at least a 20% increase in the allergen specific (CD154+) T-cell activation towards a Th1/ anergic state at week 52 DBPCFC.

13.2.2 Secondary Endpoint(s)/Outcome(s)

- Compare changes in expression of CD28+ allergen specific (CD154+) T-cells over multiple time points from baseline to week 58 and week 64 between those with sustained unresponsiveness (SU) vs those desensitized but SU failures vs those who did not pass the desensitization DBPCFC.
- Compare changes in the following measures in CD4+CD28+ allergen specific (CD154+) T-cells at week 52 and over multiple time points through week 58 between those who achieved sustained unresponsiveness (SU) vs those desensitized but SU failures vs those who did not pass the week 52 (desensitization) DBPCFC
 - Levels of IFN-gamma
 - levels of IL-4
 - Receptor diversity in allergen specific T cell CDR3b as compared to non-specific T cells
 - levels of IL-10
 - levels of TGF-beta
 - levels of GPR15
 - levels of CCR4+
 - levels of CRTh2
- Changes in distribution of immune cells representing difference in regulatory T cells vs eosinophils and mast cells over multiple time points obtained with GI biopsy tissues across those who achieved sustained unresponsiveness (SU) vs those desensitized but SU failures vs those who did not pass the week 52 DBPCFC.

Expectations:

- Comparing sustained unresponsiveness (SU) vs desensitized but SU failures, there will be at least a 50% increase in the absolute allergen tetramer + T-cell numbers at week 58.
- Comparing SU vs desensitized but SU failures. There will be at least a 20% change in the allergen specific (CD154+) T-cell activation towards a Th1/ anergic state at week 58 DBPCFC.
- Comparing desensitized vs all other failures, there will be increased IFN γ , decreased IL-4, and increased T cell receptor diversity in allergen specific T cells as compared to non-specific T cells at week 52.

- Comparing SU vs desensitized but SU failures, there will be increased IFN γ , decreased IL-4, and increased T cell receptor diversity in allergen specific T cells as compared to non-specific T cells at week 58.
- Comparing SU vs desensitized but SU failures, allergen specific T cells from participants with mild to no allergic reactions on DBPCFC at week 58 will demonstrate increased IL-10, TGF- β , GPR15, and less T cell receptor diversity.

Other Endpoints:

- Comparing the proportion of participants who become desensitized vs all others (i.e. treatment failures) at week 52 DBPCFC.
- Comparing the proportion of participants who reach SU vs desensitized but SU failures at week 58 DBPCFC.
- Comparing the proportion of participants who reach SU vs desensitized but SU failures at week 64 DBPCFC.

Safety Endpoints

- The proportion of participants with only mild AEs during the course of the study.
- The proportion of participants with respiratory or abdominal severe AEs during the course of the study.
- The proportion of participants who successfully pass a DBPCFC with no or mild objective reactions to a cumulative 2043 mg of the FA allergen at the end of OIT (week 52).
- The proportion of participants who successfully pass a DBPCFC with no or mild objective reactions to a cumulative 2043 mg of the FA allergen after 6 weeks off OIT (week 58).

Measurement: A DBPCFC is considered a “pass” if the subject has no dose limiting symptoms (appendix 3) during the challenge (from administration of first dose through observation period lasting 2 hours after administration of the final dose).

- Frequency of anaphylaxis.
- Frequency of use of epinephrine as a rescue medication.
- Frequency of AEs leading to premature withdrawal.
- Frequency of AEs in each treatment regimen leading to discontinuation of extended interval dosing.

13.3 Measures to Minimize Bias

We will use centralized laboratories and /or masking of laboratory staff to minimize bias. Because we are interested in the marginal association between CD28 expression and clinical phenotype (desensitization at 52 weeks), we will not adjust for additional covariates in the primary analysis that addresses the primary objective. Associations adjusted for sex, age and allergy type will be provided in secondary analyses.

13.4 Analysis Plan

13.4.1 Analysis Populations.

- Intent-to-treat (ITT) sample: All subjects who are enrolled will comprise the ITT sample.
- The Safety Sample (SS) is defined as all enrolled participants who receive at least one dose of OIT. Participants in the SS will be analyzed according to the treatment that they actually received. This sample will be utilized to assess differences in safety endpoints.
- We will also compare against results found in treated, mechanistic controls (n=estimate 25) with similar clinical characteristics. These historical controls will be allergen-matched and clinically

matched as best as possible to determine if they can be used to add to the mechanistic knowledge provided by the use of tetramers and CD154 testing.

13.4.2 Primary Analysis of Primary Endpoint(s)/Outcome(s)

We will rely on analysis of covariance (ANCOVA) methods to model the change of CD28 expression measured at week 52 from baseline as a continuous variable as a function of: the baseline CD28 measurement and an indicator for whether the subject passed the DBPCFC at week 52, where the parameter for the latter is of main interest and represents whether changes in expression of CD28 differ for those who achieve desensitization versus those who do not. We will test whether the parameter of interest differs significantly from zero using a two-sided F-test at the 0.05 level of significance.

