2.2. Secondary Objective(s)

- Identify, characterize, and validate new T cell epitopes for important food allergens (cashew, shrimp)
- Track the numbers and functions of epitope-specific T cells during stages of FA OIT
- Associate these parameters with phenotype and endotype characterizations in food-allergic individuals
- Determine whether immune monitoring measurements reflecting these underlying mechanisms can be used to predict responses to OIT

2.3. Exploratory Clinical objectives:

- To evaluate desensitization protocols for cashew and shrimp in allergic individuals
- Determine whether the achievement of sustained unresponsiveness is different between cashew or shrimp food allergy participants after a period of withdrawal from OIT
- Exploring changes in the transcriptomes and phenotypes of tetramer+ T cells from baseline to 52 weeks, 58 weeks, and to 64 weeks.

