13.4.4 Analyses of Secondary and Other Endpoint(s)/Outcome(s)

Similar methods will be used to address secondary objectives. For example, we will regress CD28 expression on a categorical variable for time (baseline, week 52, or week 58), a categorical variable for clinical phenotype (did not achieve desensitization, achieved desensitization but not SU, achieved SU), and their interaction to assess whether trajectories of CD28 over time are differential by response to therapy. Additionally, we will assess whether changes over time in other markers (IFN- γ , IL-4, IL-10, TGF- β , GPR15) vary by response to therapy. We will also examine whether diversity in T cell receptor status at baseline or whether changes in diversity vary by responder status.

All statistical tests will be two-sided and conducted at the 0.05 level of significance. We acknowledge, however, that we are proposing numerous secondary hypotheses and that such an approach can result in false discoveries. We will therefore be fully transparent when reporting any such findings as secondary and hypothesis generating in contrast to how the primary analysis will be reported.

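### The primary ANCOVA's pass/fail parameter compares CD28 change at equal baseline CD28 in groups formed by outcome, whereas section 13.4.2 describes it as showing whether changes differ

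*Combined protocol and SAP*

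**What the plan says.** Section 13.2.1 opens the primary endpoint with "Change in expression of CD28 in the CD4+ allergen specific (CD154+) T-cells at 52 weeks relative to baseline values" and sets it between those who pass the week 52 challenge and those who do not. Section 13.4.2 models that change on "the baseline CD28 measurement and an indicator for whether the subject passed the DBPCFC at week 52", tests the indicator with a "two-sided F-test at the 0.05 level of significance", and says its parameter "represents whether changes in expression of CD28 differ for those who achieve desensitization versus those who do not".

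Other sections bear on the same model:
- Section 13.1 describes it with a different covariate: the change in CD28 itself, not the baseline value.
- Section 13.3 explains why no further covariates enter: "Because we are interested in the marginal association between CD28 expression and clinical phenotype".
- Section 13.4.3 offers sensitivity analyses that add age, sex and allergy type.
- Section 13.4.4 regresses CD28 on time, a three-level phenotype and "their interaction to assess whether trajectories of CD28 over time are differential by response to therapy", as a secondary analysis.
- Section 3.6 rules out randomization.
- One secondary objective in section 2.2 is to "Determine whether immune monitoring measurements reflecting these underlying mechanisms can be used to predict responses to OIT".

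No section gives the baseline CD28 expected in passers and non-passers, or discusses a difference between them.

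**The concern.** With baseline CD28 in the model, the pass/fail coefficient answers this question: among participants who started at the same CD28, did passers change differently from non-passers? The text in 13.4.2 describes another: did mean change differ between the groups? In a randomized comparison the two coincide in expectation, because baseline means are equal by design. Here the groups are defined by a result observed at week 52. Nothing makes their baselines equal, and the plan itself asks whether immune measures predict that result.

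What is at stake is what a significant primary result can be said to show. Section 13.6 hypothesizes that CD28 falls more in those who become desensitized. A difference in change would point to a mechanism of OIT. A coefficient produced by a pre-existing CD28 difference would point to a predictor of response. The primary objective in 2.1 seeks both mechanistic and prognostic tools, so the report needs to tell them apart.

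**Working it through.** **Inputs.** From section 13.7: 58 passers and 14 non-passers, two measurements with compound symmetry, correlation ρ = 0.5, SD of change 0.90 and effect 0.75, all on the arcsin scale. From 13.4.2: two-sided 0.05. With equal SDs, SD of change = SD × √(2(1 − ρ)) = SD × 1, so the SD at each visit is also 0.90. The baseline difference is my assumption and is shown as a range.

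**The plan's power first.** The ANCOVA residual SD is 0.90 × √(1 − 0.5²) = 0.779. The standard error is 0.779 × √(1/58 + 1/14) = 0.232. The noncentral t with 69 df then gives 89.0% power for 0.75 (88.5% by simulation), against 87% stated. For 61 versus 11 it gives 82.6%, against 82% stated. The stated figures are therefore close to those of the baseline-adjusted model with equal baselines.

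**What the coefficient estimates.** Let week 52 CD28 have common slope b on baseline within each group. Then change = (group intercept) + (b − 1) × baseline, so

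difference in mean change = (pass coefficient) − (1 − b) × (baseline difference),

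which rearranges to

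pass coefficient = (difference in mean change) + (1 − b) × (baseline difference), passers minus non-passers.

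Compound symmetry with ρ = 0.5 makes b = 0.5. A baseline difference of 0.5 SD (0.45) shifts the coefficient by 0.5 × 0.45 = 0.225.

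**Rejection rates.** These come from 40,000 simulated trials per setting, under the inputs above. Ranges span separate runs and, in the second column, both directions of the baseline difference.

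| Baseline difference | ANCOVA rejects, mean changes equal | ANCOVA power for a true 0.75 greater fall, passers start higher |
|---|---|---|
| 0 | 4.8–4.9% | 88.5–88.7% |
| 0.1 SD | 5.2–5.4% | 84.4% |
| 0.25 SD | 7.2–7.6% | 76.3% |
| 0.5 SD | about 15% | 58.2–58.6% |
| 0.75 SD | 27–28% | 38.3% |
| 1 SD | about 42% | 21.0–21.7% |

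At 0.5 SD with equal mean changes, the rate is about 21–22% if ρ is 0.3 and 10–11% if ρ is 0.7. The difference in mean change, fitted without the baseline term, rejects about 5% in every row of the second column. Its power is about 79% in every row of the third.

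**Direction.** With equal mean changes, passers who start lower give a negative coefficient, which looks like the hypothesized greater fall. Passers who start higher give a positive one. For a true greater fall of 0.75, power rises if passers start lower: 91.7% at 0.1 SD, 95.1% at 0.25 SD and 98.0% at 0.5 SD.

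**The reverse check.** Now take as true that change is equal at the same baseline. The ANCOVA then holds its size at about 5%. The unadjusted change contrast rejects 6.7% at 0.25 SD, 12.5% at 0.5 SD and 37.8% at 1 SD.

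**The case against.** The strongest reply is that the ANCOVA is not defective. Section 13.4.2 lists baseline CD28 openly as a covariate, and for the null that goes with that model the test keeps its 5% level. The reverse check shows the change contrast failing just as badly when judged against the other null. Choosing between them in non-randomized groups is Lord's paradox, and neither choice is wrong in itself. This stands. A reader might infer that the primary test has an inflated type I error. The documents do not support that: the excess appears only against equal mean change, which is how the prose describes the target but not what the model tests.

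A reader might also infer that any baseline difference harms the analysis. It does not. At 0.1 SD the effect on size is negligible. With passers 0.1 SD higher, the ANCOVA still has more power than the change contrast (84.4% versus 78.7%), and if passers start lower its power rises.

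Nor does the reference in 13.3 to a marginal association clearly promise an analysis without baseline CD28. It explains leaving out additional covariates, and the next sentence names sex, age and allergy type. It can be read consistently with 13.4.2.

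Finally, 13.4.4 already compares unconditional trajectories, and 13.4.6 promises unadjusted associations. This helps only in part. The 13.4.4 model is secondary, has three phenotype groups and does not name the pass/fail contrast at week 52. Section 13.4.6 does not say whether unadjusted means without baseline CD28.

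**Conclusion.** The point holds as a mismatch between the parameter and its description. The coefficient in 13.4.2 is the difference in change at equal baseline CD28. It equals the difference in mean change only if the groups start at the same mean CD28 or the slope of week 52 on baseline is 1. Under the plan's ρ of 0.5, half of any baseline difference enters the coefficient.

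How much this matters depends on a baseline difference the documents do not give. It is negligible up to about 0.1 SD. At 0.5 SD, the test rejects about 15% of the time when mean changes are equal. If passers start 0.5 SD higher, power for a true 0.75 greater fall drops from about 89% to about 58%. These figures assume normal data, equal SDs, a common slope and complete measurements in 58 and 14 participants.

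Because each analysis fails under the other's null, neither alone settles whether CD28 change differs by desensitization. Both estimates and the baseline values are needed to interpret the result.

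**What to change.** Keep the ANCOVA as the primary test; alpha and sample size do not change.

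1. In 13.4.2, describe the parameter as the difference in CD28 change between passers and non-passers with the same baseline CD28.
2. In 13.1, name baseline CD28 as the covariate, to agree with 13.4.2.
3. In 13.4.3, pre-specify as supportive the two-group difference in mean change without the baseline term, with its 95% CI, and report baseline CD28 by group.
4. State that, if the two estimates diverge, the primary result will be described as an association at equal baseline that may reflect pre-existing CD28 differences.

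Do not make the primary conclusion depend on the two estimates being of similar size. The standard error of the change contrast is 0.90 × √(1/58 + 1/14) = 0.268, so its 95% CI half-width is about 1.96 × 0.268 = 0.53 against an effect of 0.75. Such a rule would add discretion after the data are seen.

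The cost is a few sentences and one extra model on data already collected. The extra analysis is less precise: about 79% power at 0.75, against about 89% for the ANCOVA with equal baselines.

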13.5.1 Interim Analysis of Efficacy Data

The interim analysis for an early evaluation of the change in CD28 from the baseline will be conducted after 30 participants are enrolled and complete the CD28 measurement at week 52. We designed the interim analysis for early stopping when we rejected the null hypothesis with a significant difference of changes on CD28 expression compared to baseline. The O'Brien-Fleming decision boundary is used to control the overall type I error probability at the conventional 0.05 level. The Lan-DeMets error-spending approach that approximates O'Brien-Fleming is used to determine the alpha with the information fraction of 41.7%. The interim analysis stage, the null hypothesis will be rejected if the test is significant at the alpha level of 0.001 with an associated absolute Z statistic of 3.28. Thus the trial will be stopped if the test statistic is less than or equal to -3.28 or greater than or equal to 3.28 with p value ≤ 0.001 ; otherwise the null hypothesis will be accepted and the trial will be continued.

Considering the possibly slow pace of participant enrollment, we will conduct our interim analysis based on data accumulated by January 31, 2021, if the pre-planned information fraction of 41.7% is not reached by that time. We will use the Lan-DeMets O'Brien-Fleming error-spending approach to determine the corresponding alpha and boundary based on the true information fraction.

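### The primary F-test is set at the full 0.05 although an interim efficacy look spends part of it and no final boundary is given; the excess error is very small, and the interim rule needs its reference distribution named

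*Combined protocol and SAP*

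**What the plan says.** Section 13.4.2 models the change in CD28 expression at week 52 on "the baseline CD28 measurement and an indicator for whether the subject passed the DBPCFC at week 52". It tests the pass/fail parameter "using a two-sided F-test at the 0.05 level of significance". It says nothing about an interim look.

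Section 13.5.1 plans one look for early efficacy stopping, which "will be conducted after 30 participants are enrolled and complete the CD28 measurement at week 52". The stated purpose of the O'Brien-Fleming boundary is to "control the overall type I error probability at the conventional 0.05 level". Lan-DeMets spending is used "to determine the alpha with the information fraction of 41.7" per cent. The null is rejected at the interim if the test is "significant at the alpha level of 0.001 with an associated absolute Z statistic of 3.28", and "the trial will be stopped if the test statistic is less than or equal to -3.28" or at or above +3.28, in either case together with a p-value of at most 0.001. If 41.7% is not reached by 31 January 2021, the look uses the data accumulated by then, and the boundary is recomputed at the true fraction.

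No section gives a boundary or nominal level for the final test. Section 13.5.1 does not name the interim test, and it words the interim null as a change in CD28 compared with baseline.

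**The concern.** A spending design fixes two thresholds. Once the interim has used some of the 0.05, the final test has to be a little stricter than 0.05 for the total to stay at 0.05. The plan prints only the interim threshold and then assigns the whole 0.05 to the named primary F-test. Taken as written, 13.4.2 and 13.5.1 cannot both hold: at a final p of 0.0499, an analyst following 13.4.2 would declare significance and one following 13.5.1 would not.

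The interim rule raises a second, smaller question. It gives a cut-off for the statistic and a cut-off for p as though they were the same thing. They are the same only if the statistic is referred to the normal distribution, whereas the only primary test that the plan names is an F-test, with few residual degrees of freedom at 30 participants. The reader is not told which reference distribution governs.

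**Working it through.** **Inputs.** Overall two-sided error 0.05; interim at 30 participants; fraction 41.7%; interim alpha 0.001 and |Z| 3.28 (all 13.5.1). Final two-sided F-test at 0.05, and a model with a baseline term and a pass/fail term (13.4.2). Total 72, planned as 58 responders and 14 non-responders (13.7).

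**1. Reproduce the interim figure.** The fraction is t = 30/72 = 0.4167, and √t = 0.6455. Two-sided symmetric O'Brien-Fleming-type spending, 0.025 per side, is

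α(t) = 4 × [1 − Φ(z₀.₉₈₇₅ / √t)].

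With z₀.₉₈₇₅ = 2.2414, the argument is 2.2414 / 0.6455 = 3.472, and the upper tail is 0.000258. So α(t) = 4 × 0.000258 = 0.00103, and the boundary is |Z| = 3.28. The plan's interim pair is correct on the normal scale.

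**2. Final boundary.** The interim and final Z statistics have correlation √t = 0.6455. Solving P(|Z₁| ≥ 3.28 or |Z₂| ≥ c) = 0.05 gives c = 1.963, a nominal two-sided level of 0.0497. The unadjusted values are 1.960 and 0.0500.

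**3. Overall error as written.** With the final test at 1.960:

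P(interim) + P(final) − P(both) = 0.00103 + 0.05000 − 0.00068 = 0.05035.

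The excess over 0.05 is about 0.00035.

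**4. Earlier look under the calendar fallback.** The same calculation at illustrative smaller interim sizes:

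| Participants at the look | Alpha spent | Final nominal level | Overall error with final at 0.05 |
|---|---|---|---|
| 30 | 0.00103 | 0.0497 | 0.0503 |
| 25 | 0.00029 | 0.0499 | 0.0501 |
| 20 | 0.00004 | 0.04998 | 0.05002 |

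The correction shrinks towards nothing as the look moves earlier.

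**5. Interim reference distribution.** The model has an intercept, baseline CD28 and the pass indicator. Thirty participants therefore leave 30 − 3 = 27 residual df (derived here, not stated in the plan). On t with 27 df:

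- |t| = 3.28 has two-sided p = 0.0029.
- p = 0.001 needs |t| = 3.69.
- p = 0.00103, the exact spend, needs |t| = 3.68.

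The rule requires both conditions. If p comes from the F-test, a statistic between 3.28 and 3.69 fails the p condition and the trial does not stop. The p condition binds, and 3.28 has no effect.

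**6. Simulation check.** Four million null ANCOVA data sets were generated, with an assumed 24/6 split at the interim and 58/14 at the end. With p ≤ 0.001 applied at the interim, interim error was 0.0010 and overall error 0.0504 with the final test at 0.05 (standard error about 0.0001). With 3.28 applied alone to the t statistic, the figures were 0.0029 and 0.0514.

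**The case against.** The best defence is that 13.5.1 already commits the trial to 0.05 overall and names the spending function. That determines the final boundary once the actual fraction is known, so the 0.05 in 13.4.2 may be meant as the overall level. This reading is possible, but the text does not give it: 13.4.2 attaches 0.05 to a single named test of a single parameter. What stands is that the practical difference is tiny. It affects only a final p between 0.0497 and 0.0500, and less than that if the look came early.

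A reader might infer that the interim rule itself inflates the error by pairing a normal cut-off with an F-test. The documents do not support that. Section 13.5.1 calls 3.28 a Z statistic, does not name the F-test at the interim, and requires p ≤ 0.001 as well. The 0.0029 interim spend arises only if the p condition is dropped and 3.28 is applied to a t statistic.

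A reader might also infer that 41.7% is the wrong information fraction, because information on a pass/fail contrast depends on how many pass. At the planned pass proportion π the ratio is 30π(1 − π) / 72π(1 − π) = 30/72, so the planning figure is right. Other splits would be hypothetical.

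Finally, the 0.05 sentence in 13.4.4 is not evidence on the final primary level, because that section covers secondary and other endpoints.

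**Conclusion.** The point holds, and its size is very small. The plan claims 0.05 overall, sets its final primary test at 0.05 after an efficacy look that spends alpha, and gives no final boundary. With the look at 30/72, the final level should be 0.0497, and the error as written is about 0.0503. This rests on normal theory and on reading 13.4.2 literally.

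The interim pair is correct on the normal scale but is not tied to a test. If the test is the ANCOVA F-test on 27 df, the written rule still holds the interim error at about 0.001 through its p condition. That part is therefore a matter of clarity and not a demonstrated inflation.

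The figure 0.0497 should not be treated as fixed. This protocol version is dated 26 May 2022, after the fallback date of 31 January 2021, and the documents do not say whether the look took place or at what fraction.

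**What to change.** In 13.4.2, replace the flat 0.05 with a final nominal level derived from the Lan-DeMets O'Brien-Fleming function and the alpha actually spent, and cross-refer to 13.5.1. The level is 0.0497 (|Z| = 1.963) if the look was at 30/72, and closer to 0.05 if it was earlier under the fallback.

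In 13.5.1, name the interim test and its null hypothesis. Express the boundary only as a nominal p-value from that test (0.00103 at 30/72, recomputed at the true fraction under the fallback), and remove the ±3.28 cut-off. If the look has already been made, record the fraction, the test and the alpha used, since the rewording would then serve only as documentation.

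The cost is a few sentences and a very slightly stricter final level. No extra participants are needed.
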